5.1.2 Secondary Outcomes

(1) pre-operative frailty, (2) exercise capacity, (3) physical activity behavior, (4) in-hospital outcomes, (5) 1-year clinical outcomes, (6) 1-year health-related quality of life, (7) cost-analysis.

5.2 Statistical/Analytical Plan

Objective 1: To determine if *Prehab* reduces the proportion of frail elderly patients requiring a prolonged hospital length of stay of >7 days. A univariable analysis will be undertaken to determine if hospital *LOS* > 7 days is associated with frailty and other patient-level factors. A stepwise multivariable logistic regression model will then be developed to determine if *Prehab* attendance is independently associated with a decreased risk of prolonged hospital length of stay > 7 days. As a secondary analysis, hospital *LOS* will also be compared as a continuous variable between the *Prehab* and standard care groups using a Mann-Whitney test.

“The PREHAB Study” (Pre-operative Rehabilitation for reduction of Hospitalization After coronary Bypass and valvular surgery.)

Objective 2: Does attending *Prehab* influence frailty, exercise capacity, physical activity behavior, in-hospital complications, and *HRQoL*? Although we will employ four different measures of frailty, based on our preliminary data and based on a Task Force’s position statement(90), the Modified Fried Criteria will be the primary frailty outcome over time from baseline to the end of *Prehab* program (pre-operatively), or from baseline to the 3-month post-operative follow-up. The primary measure of exercise capacity will be the *6MWT* and will be analysed with univariable linear regression models to evaluate the association between the *6MWT* and *Prehab* attendance. Accelerometers will be used to objectively measure the number of minutes spent performing moderate to vigorous physical activity (*MVPA*) and total physical activity (*TPA*) per day for a period of 7 days and compared between groups. A composite outcome for a major adverse cardiac event (i.e. *MACCE* = in-hospital stroke, myocardial infarction, renal failure requiring dialysis and death) and delirium will be compared between groups using a Chi-Square or Fisher’s Exact test. A multivariable logistic regression will be used to identify if *Prehab* is independently associated with in-hospital delirium. The *SF-12v2* and *EQ-5D* scores, after normative standardization, will be analyzed through use of a repeated *ANOVA* to allow for a standardized group and group/time interaction effect estimation.

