3.2 Study Design, Setting, Population

Prehab will be a five centre prospective, randomized, open, blinded endpoint (*PROBE*) (47) controlled trial using assessor blinding and intention-to-treat analysis. The study will be conducted at four academic, tertiary care hospitals (St. Boniface Hospital, Winnipeg, MB, Queen Elizabeth II Health Sciences Centre, Halifax, NS, Montreal Heart Institute, Montreal, QC, Quebec heart and lung institute, Saint-Foy, QC) and one non-academic hospital (Saint John Regional Health Centre, Saint John, NB) that perform cardiac surgery. These sites were chosen based on similar patient populations and surgical waitlist times (48)(49). Additionally, each of these sites are partnered with one or more community-based cardiac rehabilitation (*CR*) centres, which are certified medical fitness facilities dedicated to improving the health of the community through health promotion, disease prevention and rehabilitation services. These facilities offer expert guidance from certified professionals, innovative health enhancement programs, and provide integrated medical, rehabilitative and fitness services.

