3.5.3 Randomization

Trial Randomization using *REDCap*: The Randomization Module within *REDCap* allows researchers to randomly assign participants to specific groups. [name] has experience and will be responsible for study randomization. Assessors of pre- and post-operative data will be blinded to treatment group allocation.(47)

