5.3 Sample Size Calculation

The sample size calculation was based on the primary objective – determining the effect of *Prehab* on rates of prolonged hospital length of stay > 7 days. Our preliminary data, demonstrated the proportion of frail patients in the Control group with a hospital length of stay > 7 days to be 58.3%. For the *Prehab* group, based on improvements in functional capacity in our pilot *RCT* and the work by Arthur et al14, we believe an absolute 20% reduction in proportion of patients that require prolonged hospital length of stay of greater than 7 days, is feasible. A sample size of 194 individuals (97 in each group) will be required for a two-tailed test at an alpha of 0.05 and power of 80%. All patients assigned to the pilot *Prehab* group completed the intervention, however, we are mindful that we will be recruiting frail, elderly patients who may have a higher dropout rate. Hence, we are estimating a 20% dropout rate and plan to recruit 244 individuals (122 in each study arm) to achieve an eventual sample size of 194 after dropout.

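### Site is not specified as a randomization stratum and is not kept in the primary model, so balance within site and possibly a little power are given up at almost no saving

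*Combined protocol and SAP*

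**What the plan says.** On allocation, section 3.5.3 says only that the REDCap module "allows researchers to randomly assign participants to specific groups". It mentions no strata, block sizes or site factor.

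On analysis, section 5.2 (Objective 1) first asks by univariable analysis whether a stay over 7 days "is associated with frailty and other patient-level factors", then develops a stepwise multivariable logistic model. No covariate is forced in and site is not named. The secondary Mann-Whitney comparison of length of stay is also unstratified.

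Other places that bear on the point:

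- Section 3.2: four academic hospitals and one non-academic hospital. "These sites were chosen based on similar patient populations and surgical waitlist times"; length of stay is not among the selection grounds.
- Synopsis: the 244 patients are to be split evenly over the five sites.
- Section 8.7 (Research Assistants): one site is staffed from one year after study launch and another joins two years after launch.
- Section 3.4.1: patients are assessed daily against standardized readiness-for-discharge criteria. Section 5.1.1 nevertheless defines the endpoint as plain hospital stay over 7 days.
- Section 6: each patient is given a site code.

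**The concern.** Whether a patient is still in hospital on day 8 is partly a matter of local discharge practice, and under section 3.5.4 control care is whatever each site currently delivers. Site is thus a plausible predictor of the endpoint. It is known before randomization and already recorded. If allocation ignores it, a site with unusually long or short stays may by chance send more patients to one arm. If the analysis also ignores it, that chance difference stays in the estimate and any between-site variation goes unused. Stepwise selection adds a further weakness: even if site were offered to the model, nothing would keep it there.

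**Working it through.** **1. The plan's own figure.** Section 5.3 gives a "two-tailed test at an alpha of 0.05 and power of 80"%, a control rate of 58.3% and an "absolute 20% reduction in proportion of patients that require prolonged hospital length of stay of greater than 7 days", so 38.3% under Prehab. With pooled variance under the null:

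n per arm = [1.960·√(2·0.483·0.517) + 0.842·√(0.583·0.417 + 0.383·0.617)]² / 0.20² = (1.385 + 0.583)² / 0.04 = 96.8, so 97.

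Power at 97 per arm is 80.1%. Allowing for dropout, 97/0.8 = 121.25, so 122 per arm and 244 in all. Both figures reproduce.

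**2. Balance within site.** An even split gives 244/5 = 49 recruited per site. Under unstratified 122:122 allocation the SD of the arm difference within a site is √(49·195/243) = 6.3 patients. The chance of a 60:40 or worse split is 11% per site (15% under simple randomization); the simulated chance that at least one of five sites is split this badly is 42%.

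Smaller sites fare worse. Under simple randomization, a 16-patient site has a 2·P(X ≥ 11) = 21% chance of 11:5 or worse, and a 10-patient site a 2·P(X ≥ 7) = 34% chance of 7:3 or worse.

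Small sites are likely on the plan's own dates. Section 9 has recruitment from October 2014 to 1 December 2015. If launch means April 2014, a site opening one year later has about eight months left; if it means October 2014, about two. A site opening two years after launch starts after planned recruitment has ended on either reading.

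**3. Power.** Between-site variation is not in the documents, so it is an assumption, shown over a range. There were 40,000 simulated trials per row, with 194 evaluable patients in five near-equal sites, marginal rates 58.3% and 38.3%, and a common within-site odds ratio. A: unstratified allocation, unadjusted test. B: unstratified allocation, site-adjusted test. C: site-stratified allocation, site-adjusted test. The adjusted test is Cochran-Mantel-Haenszel, standing in for a logistic model with site forced in. Simulation error is about √(0.8·0.2/40,000) = 0.2 points.

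| Site SD (log-odds) | Site control rates | A | B | C | C minus A* | Conditional OR |
|---|---|---|---|---|---|---|
| 0 | 58% | 80.7% | 79.3% | 81.0% | 0.3 | 2.25 |
| 0.25 | 50–67% | 80.7% | 79.9% | 81.2% | 0.5 | 2.28 |
| 0.5 | 41–74% | 80.9% | 81.8% | 82.3% | 1.3 | 2.37 |
| 0.75 | 34–81% | 80.9% | 83.9% | 84.3% | 3.5 | 2.52 |
| 1.0 | 27–86% | 80.9% | 87.2% | 87.8% | 6.9 | 2.73 |

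*Points, taken before rounding.

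At SD 0.8, separate runs of 10,000 trials for A against B gave 80.3% against 84.1% with equal sites, and 80.2% against 83.2% with assumed sizes 80/50/40/16/8.

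**4. Validity.** Type I error under A is 4.8 to 5.1% over the whole range. If allocation were stratified but site left out of the analysis, the unadjusted test would become conservative: 4.3% at SD 0.5 and 3.0% at SD 1.0. Stratifying and adjusting therefore belong together.

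**5. Baseline predictor.** A moderate predictor such as EuroSCORE II (assumed log-odds 0.6 per SD) adds about 2 to 3 points. This is separate from site.

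**The case against.** Several stronger readings are tempting, and the documents do not support them.

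- **That the trial is unstratified.** Section 3.5.3 is silent on the allocation scheme, and the process chart (Figure 4) is not available in the text. Stratification is not specified; its absence is not established.
- **That site cannot enter the model.** The patient-level wording describes the univariable screen. The sentence on the stepwise model lists no permitted or barred candidates. Site is not named and not forced in, which is a weaker statement.
- **That the precision gain is free.** It depends on unknown between-site variation. Where sites do not differ, adjustment without stratified allocation loses about 1 point (80.7% against 79.3%). The sites were chosen as similar, and the readiness-for-discharge criteria may narrow differences further. They do not remove the point, because the endpoint in section 5.1.1 is not defined by them.
- **That the treatment estimate is biased.** Imbalance under randomization is chance error that the test already allows for. A 16-patient site split 11:5, with a rate 25 points from the average, shifts the risk difference by about (6/97)·0.25 = 1.5 points, against a standard error of √[(0.583·0.417 + 0.383·0.617)/97] = 7.0 points.
- **That adjustment shrinks the error term.** In logistic regression, adjusting for site moves the target to a conditional odds ratio further from 1. It does not reduce the standard error of the log odds ratio.

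The even split in the synopsis is also a fair reply on small sites, but it is hard to reconcile with sections 8.7 and 9. What survives is that a recorded, plausibly prognostic design variable has no secured role in allocation or analysis, and that securing one is cheap.

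**Conclusion.** The point holds as a low-cost improvement, not as a defect of validity. Site-stratified randomization is not specified, and the primary model does not retain site. The sample size stands and type I error is held.

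The loss is balance within site, which matters most if late-opening sites stay small, and possibly some power. Using site in both allocation and analysis gains about 0 points if sites do not differ and 1 to 2 at a site log-odds SD of 0.5. At 0.8 I put it at about 2 to 5, depending on site sizes and on whether allocation is stratified. These figures rest on assumed between-site variation and a common within-site odds ratio. The further 2 to 3 points from EuroSCORE II should not be credited to site. With planned power at 80.1% there is little reserve, so even a small gain is worth taking.

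**What to change.** In section 3.5.3, specify a REDCap allocation table stratified by site, with permuted blocks of varying size so that the next assignment is hard to predict in this open-label trial. Avoid crossing site with procedure type if sites are small: that makes 5 × 2 = 10 strata, and many blocks would stay incomplete.

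In section 5.2, replace stepwise selection for the primary comparison with a logistic model of randomized arm plus site, procedure type and EuroSCORE II, all pre-specified and unselected. State in advance how very small sites are merged, for example those with fewer than about 10 patients. Report the risk difference, for example by standardization from that model, alongside the conditional odds ratio, because section 5.3 sizes the trial on an absolute difference.

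The cost is one allocation table and a few sentences; every variable is already collected. The downside is a few extra model terms and, if allocation is not stratified and sites turn out not to differ, a loss of about 1 point of power.

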Study Sites (with site lead contact information):	
St. Boniface General Hospital [name]/[name] CR3012-I.H. Asper Institute [name] [contact] [contact] Email: [contact]
 
Saint John Regional Hospital - New Brunswick Heart Centre [name] [name] [contact] Email: [contact]
 
Queen Elizabeth II Health Sciences Centre [name] [name] [contact] [contact] Email: [contact]
 
Montreal Heart Institute [name] [name] [contact] Email: [contact]
 
Quebec Heart and Lung Institute (University of Laval) [name] [name] [contact]) Email: [contact]
	
Study Design:	A five centre prospective, randomized, open, blinded endpoint (PROBE) controlled trial using assessor blinding and intention-to-treat analysis.	
Expected number of participants:	244 individuals (122 in each arm) split up evenly between five study sites.	
Intervention:	Patients in the Prehab group will receive, in addition to the standard of care, a	

“The PREHAB Study” (Pre-operative Rehabilitation for reduction of Hospitalization After coronary Bypass and valvular surgery.)

	
four to eight-week comprehensive exercise therapy and education program at a community-based CR facility (see details in appendix). Patients will be asked to complete at least two sessions of supervised, structured exercise class plus have the option to attend one additional exercise class per week for a minimum of four weeks up to the time of their surgery, with progression to a moderate to high-intensity interval program based on the supervised assessment of the patient’s capabilities.
 
Prehab participants will also attend four education sessions on topics such as risk factor reduction, medication use, cardiovascular physiology, smoking cessation, healthy eating, exercise, and stress management and promotion of self-managed care.

Duration per participant:	~ 4-8 weeks

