Briefly, patients will be required to attend a minimum of 2 structured exercise sessions per week. The program will last a total of 8 weeks, or until the patient undergoes their cardiac procedure (minimum of 4 weeks for data collection purposes). Patients will be encouraged to walk daily in addition to attending the scheduled exercise sessions. Exercise will be prescribed according to standardized procedures at the medical fitness facility for their cardiac rehabilitation program. Briefly, participants will complete a warm-up/stretching session of approximately 15 minutes at the beginning of each session. Aerobic exercise will be prescribed at 40-60% of heart rate reserve (Karvonen Formula) based on baseline exercise stress test data. Aerobic exercise will last approximately 10-30 minutes depending on individual tolerance and level of conditioning. Aerobic prescription will progress to high intensity exercise in the context of symptom-limited, interval training up to 85% of maximal aerobic capacity based upon recommendations by the cardiologist. Individual interest will determine the modality of exercise chosen. Options will include walking, cycling, stretching and resistance training with body weight or resistance bands following clearance by a cardiologist. Intensity will be progressed based on close communication between healthcare providers and participants. Sessions will be concluded with a 10-minute cool down period.

In addition to the exercise program, patients will be required to participate in 4 educational sessions tailored to self-management for cardiac rehabilitation. Examples of educational sessions offered by professional staff at the medical fitness facility include:

- Exercise and Action Planning (Kinesiologist)
- Risk Factor Modification (Nurse/Physiotherapist)
- Cardiac Electrical System (Nurse/Physiotherapist)
- Cardiac Circulation (Nurse/Physiotherapist)
- Cardiac Muscle Function (Nurse/Physiotherapist)
- Resistance Training (Kinesiologist)
- Body-Mind Connection (Social Worker)

“The PREHAB Study” (Pre-operative Rehabilitation for reduction of Hospitalization After coronary Bypass and valvular surgery.)

Heart Healthy Eating (Dietician)
Looking Forward; transitions, barriers, self-management (Kinesiologist)
Diabetes Education (Dietician)
Emotional Impact of Heart Disease (Social Worker)
Label Reading (Dietician)
Preventing Relapse (Social Work)
Stress Busters (Psychologist)
Tracking Food Choices (Dietician)

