Smoking Cessation (Social Worker)
Relaxation Techniques (Psychologist)

Participants in the intervention group will be asked to keep a log of their attendance at both the exercise and educational session. Additionally, an exercise log completed by individual patients will track the mode of exercise completed in addition to monitoring compliance with the intervention.

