3.5.6 Variable Waitlist Time

We acknowledge that the time on the waiting list may be variable. For example, in Manitoba the median waitlist time is 12 weeks (range: 3-31 weeks). The median waitlist time for our preliminary study was 62 days and such we believe that enrolled patients will not be subjected to any undue harm. The recommended standard wait for elective cardiovascular surgery should not exceed six weeks,(86) however the best physiological outcomes for patients attending cardiac rehabilitation is at least eight weeks(21)(19)(20)(79), or occur by participants who attend more than 25 sessions of *CR*.(11) After consulting with the associated *CR* program sites and our expert co-investigators, it was determined that the preferred *Prehab* intervention would be 8 weeks because it was deemed that clinically stable, frail, elderly patients could feasibly achieve measurable health benefits and risk factor modification over this

“The PREHAB Study” (Pre-operative Rehabilitation for reduction of Hospitalization After coronary Bypass and valvular surgery.)

time frame.(87) However due to the variability in the waitlist times participants would still be eligible with a waitlist time of 4 weeks minimum.

What if patients are unable to complete the Prehab program due to a change in surgical date?

It is possible that a patient may not complete the full 8 week program due to scheduling changes for their procedure. We and others (78)(11)have seen functional and health behavior improvements in as little as 2-4 weeks. Notably, 2 patients in our pilot *Prehab* project participated in the program for only 3.5 weeks but still improved their total distance walked by an average of 174 meters (43% improvement). Our data is supported by Fiorina and associates and indicates that as few as 15 days of *CR* can improve total distance walked by as much as 40%. With this in mind, the *Prehab* program has been structured to provide the more intensive nutritional counselling, educational, psychosocial and exercise therapy during the first four weeks of the program and engage *Prehab* participants to take control of their self-managed care for the remaining program. This will enable participants to gain meaningful benefits in the event scheduling changes prevent the completion of the 8 week program.

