3.5.6 Qualitative review of PREHAB Study

We engaged patients prior to conducting the PREHAB study to uncover whether patients would participate in a prehabilitation intervention. After study completion we want to continue the conversation with all patients both in the intervention arm, standard care arm as well as registry participants.

During the post study intervention we will conduct a series of individual interviews and survey components to enlist patient-centered response and opinion to the study intervention. We wish to know if there were barriers for participation, any factors that reduced adherence to the study as well as an overall satisfaction with the intervention. We also would like to discuss how improvements can be made after a participant has finished the intervention part of the study. For non-intervention patients we want to see if they went to cardiac rehab post-surgery and what its impact was on their recovery.

Additionally, A small group of participants and their caregivers from the primary site will be contacted and asked to participate in a more extensive patient panel session to better understand the patient valued experience of the intervention that was provided to participants and ways to improve delivery and adherence. We will conduct 3 group sessions of patients and their caregivers lasting approximately 2-3 hours. We will be following a general format with topic questions; however, we expect a very open conversation. All information will be transcribed and stored. Information identified within these sessions may be used to develop tool to be used to improve communication and adherence to care based interventions during the perioperative process. (See PREHAB Patient panel protocol)

We will conduct interviews with patients based on availability. As we are a multi-site intervention we will interview patients from the study who are not local to the primary site. We will contact current participants and enroll patients who are interested in the study. We will also identify patient perspective with cardiac rehabilitation post-surgery .

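### Section 5.2 analyses the primary outcome through a stepwise model of an undefined Prehab attendance; no comparison of LOS >7 days by randomised arm is stated, and nothing keeps the treatment term in the model

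*Combined protocol and SAP*

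**What the plan says.** The synopsis and section 3.2 describe a "controlled trial using assessor blinding and intention-to-treat analysis". The primary outcome (section 5.1.1) is binary: hospital LOS above 7 days.

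Under Objective 1, section 5.2 gives two steps for that outcome. The first is a univariable analysis of frailty and other patient-level factors, which does not name the arm. The second is: "A stepwise multivariable logistic regression model will then be developed to determine if *Prehab* attendance is independently associated with a decreased risk". Candidate covariates, entry and removal rules, and a forced treatment term are not given. The only LOS comparison stated by group is on days and is labelled secondary: "hospital *LOS* will also be compared as a continuous variable between the *Prehab* and standard care groups using a Mann-Whitney test".

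Attendance is recorded separately from allocation (section 3.5.5): "Participants in the intervention group will be asked to keep a log of their attendance at both the exercise and educational session". The same section mentions two sessions a week, four education sessions, and a programme of 8 weeks "or until the patient undergoes their cardiac procedure (minimum of 4 weeks for data collection purposes". None of these is tied to the word used in section 5.2.

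Section 3.5.6 (Variable Waitlist Time) allows for incomplete programmes: "It is possible that a patient may not complete the full 8 week program due to scheduling changes for their procedure". The section on the qualitative review plans to ask about adherence: "We wish to know if there were barriers for participation, any factors that reduced adherence to the study".

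**The concern.** A trial analysed by intention-to-treat compares the groups as randomised. A model whose exposure is attendance compares people who came with people who did not, and those may differ in prognosis. The bias favours Prehab if sicker patients attend less and goes against it if healthier patients attend less. With no definition fixed in advance, the cut-off could also be chosen after the data are seen.

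A second problem remains even if the word means assigned arm. A stepwise procedure may remove any term that is not forced in. A trial with a weak or null result could then end with no estimate and no confidence interval for its primary comparison.

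**Working it through.** **1. The sizing in section 5.3.** Inputs: 58.3% against 38.3%, two-sided alpha 0.05, power 80%.

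n per arm = [z₀.₉₇₅ √(2p̄(1−p̄)) + z₀.₈₀ √(p₁(1−p₁) + p₂(1−p₂))]² / (p₁−p₂)², with p̄ = 0.483
= (1.3851 + 0.5827)² / 0.04 = 96.8, so 97 per arm and 194 in total.

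Dropout: 97/0.80 = 121.25, so 122 per arm and 244 in total. Both match the plan. The sample size therefore rests on an unadjusted comparison of two proportions by arm, a test that section 5.2 does not name for this outcome. Section 5.2 does name a Chi-Square or Fisher test between groups for MACCE and delirium.

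**2. What attendance could mean.**
- Towards assigned arm: Objective 1 asks whether Prehab reduces the proportion. Objective 2 opens by asking what attending Prehab influences and then compares activity, MACCE and delirium between groups. Section 3.5.2 repeats the 6MWT in control and Prehab patients to judge the intervention's impact.
- Towards sessions attended: attendance is logged on its own, and the models for LOS >7 days and for the 6MWT both use the word, whereas the delirium model refers only to Prehab.

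The first reading is the more natural one; the text does not settle it.

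**3. If it means arm.** The plan gives no selection rules, so these are assumed: 97 per arm, 10 covariates of which 5 are prognostic, entry at p<0.05, removal at p≥0.10, arm selectable, 600 simulated trials. The arm term stayed in the final model in 84% of trials with about a 20-point effect and in 6% with none (unadjusted rejection under no effect: 5.5%). So false positives barely rise, but no arm estimate remains in about 16% and 94% of trials respectively.

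**4. If it means sessions attended.** Assumptions: no true effect, 58.3% risk in each arm, 122 per arm, 20% non-attendance (24.4 patients, leaving 97.6 attenders), non-attender risk q.
- Attenders' risk: pₐ = (0.583 − 0.2q)/0.8.
- Non-attenders counted as unexposed: comparator risk = (122×0.583 + 24.4q)/146.4.
- Non-attenders excluded: comparator risk = 0.583, n = 122.
- Type I error = Φ((d − 1.96·SE₀)/SE₁) + Φ((−d − 1.96·SE₀)/SE₁), where d is comparator risk minus pₐ, SE₀ is pooled and SE₁ unpooled.

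| q | pₐ | d, unexposed | Type I | d, excluded | Type I |
|---|---|---|---|---|---|
| 50% | 60.4% | −3.5 points | 8% | −2.1 | 6% |
| 58.3% | 58.3% | 0 | 5% | 0 | 5% |
| 70% | 55.4% | 4.9 | 12% | 2.9 | 7% |
| 75% | 54.1% | 7.0 | 19% | 4.2 | 10% |
| 80% | 52.9% | 9.0 | 29% | 5.4 | 13% |

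These figures are unadjusted. In simulation with non-attenders counted as unexposed, a prespecified adjusted model that included the cause of non-attendance gave 5.3/4.5/5.0% at risks of 70/75/80% (4,000 runs). That is near nominal.

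**5. Power by arm.** If a fraction of the Prehab arm gains nothing (assumption), the 20-point difference shrinks in proportion: 20 × 0.8 = 16 points at 20%.

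| Gaining nothing | Difference | 122 per arm | 97 per arm |
|---|---|---|---|
| 0% | 20 points | 88% | 80% |
| 10% | 18 | 81% | 71% |
| 20% | 16 | 71% | 61% |
| 30% | 14 | 59% | 50% |

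**The case against.** The best reply is that this is drafting shorthand. Intention-to-treat is stated twice, the sizing is by group, and Objective 2 uses attending Prehab to introduce between-group comparisons. The log in section 3.5.5 is there to monitor compliance and is never named as a model exposure. Most of this stands, and it makes assigned arm the likelier reading. It does not remove the gap: a general principle does not repair a primary model that names a different, undefined exposure, and it does not force the treatment term in.

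A reader might go further and infer that pilot non-attendance was 25%, because "2 patients in our pilot *Prehab* project participated in the program for only 3.5 weeks" and the pilot randomised 8 to Prehab. The documents do not support that. Those two patients did take part, for a shorter time, and the paragraph concerns changed surgery dates. Section 5.3 and the appended pilot report have all 8 completing; section 3.1.1.2 gives 88%. None of these is a non-attendance rate for this trial, and none says anything about the prognosis of non-attenders.

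It is also fair to object that the 12/19/29% figures use the less favourable coding and no adjustment. Excluding non-attenders roughly halves the excess at the higher risks, and the protocol collects extensive baseline frailty, comorbidity and cardiac data that could be adjusted for.

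**Conclusion.** The point holds as a defect of specification in the primary analysis and should be fixed. The exposure is undefined, the binary primary outcome has no stated comparison by arm, and the treatment term may be dropped. Under the likelier reading the harm is limited to a possible missing estimate and CI, since selection adds little type I error. Under the literal reading randomisation no longer protects the comparison. Type I error could then reach 7–13% or 12–29%, depending on how non-attenders are coded, but only under the assumed 20% non-attendance, the assumed 70–80% risk and no adjustment. It is 5% if risks are equal and near nominal if the cause of non-attendance is measured and adjusted for.

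A reader might infer that the trial has abandoned intention-to-treat or that its result will be biased towards Prehab. The documents support neither: the wording is ambiguous, and the size and direction of any bias are unknown. The sample size is not in error.

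**What to change.** In section 5.2:
- Replace attendance with randomised arm for LOS >7 days and for the 6MWT.
- State the primary analysis as a comparison of LOS >7 days by assigned arm, regardless of sessions attended, two-sided at 0.05, reporting the difference in proportions with its 95% CI. This matches section 5.3.
- Drop stepwise selection. Any adjusted logistic model should force in arm and a short prespecified list of baseline covariates already collected. Whether the adjusted or the unadjusted test is primary is the sponsor's choice, provided it is fixed in advance.
- Keep attendance as a labelled supportive analysis with its cut-off defined beforehand.

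This changes wording only. LOS comes from site databases and charts for both arms, so no new data are needed. The cost is a possibly diluted effect: if 20% of the Prehab arm gain nothing, unadjusted power is about 71% at 122 per arm. It is about 61% at 97 per arm, the number left if the planned 20% dropout also have no LOS. That is the power of the intention-to-treat analysis the protocol already promises.
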